4.1 Description of the Trial Design

The trial is an open label, F	H dose esc	calation t	rial	to assess the	safe	ty and	d tolerab	ility a	s well as
immunogenicity/preliminary	antitumor	activity	of	ES2B-C001	with	and	without	the	adjuvant
in patients with				breast car	ncer				
. The trial is planned	in a single	center in	Aus	stria. The IMP	ES2	B-C0	01, in cor	mbin	ation with
[adjuvant] , is de	fined as the	adjuvar	ited	IMP or the a	djuva	nted E	S2B-C0	01, 0	or without
[adjuvant] define	ed as the	non-adju	ıvar	nted IMP or	the n	on-ac	djuvante	d ES	2B-C001
throughout the protocol.									

The overall trial design is illustrated in Figure 1.

Clinical Study: ES2B-C001-S01 EU CT No.: 2024-516333-12-00

The study is expected to be completed within 15 months according to the interventional periods described below:

For each patient enrolled, there will be a:

Screening period:

The screening period starts upon signing the Informed Consent Form (ICF) by a patient and lasts for a maximum of 28 days. During this period a patient will undergo procedures for evaluation against study inclusion and exclusion criteria. Tumor imaging does not need to be repeated if it was performed before the ICF was signed but within the screening period as standard of care.

Treatment period:

Each patient will be dosed

Safety follow-up for ~6 weeks following last dose of ES2B-C001.

The trial design envisions a total of 3 cohorts. The dose escalation will be conducted according to an adapted 3+3 design. Three dose level cohorts are planned for the adjuvanted ES2B-C001. The number of patients included in one dose cohort is 3 but may be increased from n=3 to n=6 or n=9 in each of the cohorts. Eligible patients may be added at lower dose levels via "backfilling" allowing patients access to the study and potentially providing a larger sample size for exploratory immunogenicity testing.

Dose cohorts are described in Table 4. The preparation and exact dose volumes of the IMP are detailed in the IMP manual.

Table 4: Description of the ascending-dose cohorts, and respective route of administration (Cohort 1-3)

4.2 Rationale for Trial Design

This Phase 1 clinical trial is designed to determine safety, and tolerability of adjuvanted and non-adjuvanted ES2B-C001 to establish a maximum tolerated dose for this novel HER2-directed

Clinical Study: ES2B-C001-S01 EU CT No.: 2024-516333-12-00

vaccine in breast cancer patients. The primary rationale for conducting such phase 1 studies is to obtain sufficient information about safety and preliminary efficacy such as immunogenicity and antitumor activity to permit the design of subsequent well-controlled, scientifically valid phase 2 studies. The number of subjects included in such phase 1 trials is small, just enough to determine the safety, proper tolerated dose, and method of administration of the IMP, with or without adjuvant, for a next phase study. Enrollment in this FiH trial will be fully staggered in each of the populations. Repeated safety evaluations will be conducted during pre-dosing calls between PI(s), CRO medical monitor, and Sponsor, where safety and reactogenicity data from the first patient of each cohort will be reviewed. Additional safety evaluations will be performed at DSMB meetings to ensure a progression according to 3+3 design through a limited number of dose levels guided by safety. After accumulation of safety data across the dose levels, a maximum tolerated dose (MTD) will be established or if no unacceptable side effects or DLTs occur up to the highest dose level cohort, MTD will be determined as the maximum administered dose (MAD) level.

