Expansions of the cohorts are foreseen without further amendment. Expansion of cohorts will be considered in the case of high variability of the emerging immunogenicity data or in case it appears desirable to obtain more safety data from a given cohort.

Patients will be considered to have completed the study protocol if they attend an end of study (EOS visit) 6 weeks after the last dose of the primary vaccination series.

Booster doses may be offered to patients under a compassionate use program (CUP) based on the investigator's choice for patients with at least stable disease or better who show a good immunologic response and a good tolerability, if they wish to receive such boosters.

Test Product ES2B-C001:

Type: Vaccine

Formulation: solution for intramuscular injection

Strength: 3.0 mg/mL

Route of administration: intramuscular (I.M.)

Medicinal Product (IMP)

Investigational

Type: Adjuvant

[figure not shown]
Formulation: 3.0 mL solution; mixed in 1:1 (v/v) ratio with ES2B-C001

	Strength: N/A
	Route of administration: intramuscular (I.M.)
Number of Participants	9 patients (3 per cohort) will be enrolled in the dose escalation parts with 3 dose levels each. Up to 3 expansions of cohorts are planned, which may increase cohort sizes to 6-9 patients. In total, up to 27 patients may be dosed (not accounting for replacement of potential dropouts).
Inclusion Criteria	Subjects who meet the following criteria will be eligible to participate in the clinical study:
Exclusion Criteria	Subjects who meet one or more of the following criteria will not be considered eligible to participate in the clinical study:

Clinical Study: ES2B-C001-S01 EU CT No.: 2024-516333-12-00

expreS2ion BIOTECH

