2.4 Overall Benefit-Risk Conclusion

In conclusion, this trial aims to evaluate the safety profile of the novel HER2-directed vaccine ES2B-C001 with and without adjuvant. The risks for the patients participating in the trial are considered low and it is expected that the polyclonal anti HER2 antibody response will have anticancer effects beneficial to patients participating in the trial. The overall risk-benefit-ratio of participating in this trial is judged to be favorable in patients

3 Trial Objectives and Endpoints

Table 3: Description of the objectives and endpoints of this clinical study.

Objectives	Endpoints			
Primary				
To determine the safety, tolerability, maximum tolerated dose (MTD) for ES2B-C001 alone or in combination with the adjuvant	 Nature and frequency of dose-limiting toxicities (DLTs). Incidence, nature and severity of AEs graded according to the National Cancer Institute (NCI) Common Terminology Criteria for Adverse Events (CTCAE) v5.0. Incidence, nature and severity of injection site reactions according to FDA Guidance on Toxicity Grading Scales in Vaccine Trials (FDA, 2007). 			

Clinical Study: ES2B-C001-S01 EU CT No.: 2024-516333-12-00

Objectives	Endpoints			
Secondary				
To investigate the immunogenicity of ES2B-C001 alone or in combination with the adjuvant	 Immunogenicity as humoral immune response: Total anti-HER2 Immunoglobulin titers in sera by enzyme-linked immunosorbent assay (ELISA). Isotyping of anti-HER2 Immunoglobulins in sera (e.g. IgM, IgG (IgG1-4), IgD, IgE, IgA), Optional and obligatory in the non-adjuvanted and adjuvanted treatment group, respectively. 			
Exploratory				
To determine the preliminary antitumor activity of ES2B-C001 alone or in combination with the adjuvant observed	 Percentage of patients with measurable disease at baseline achieving Complete Remission (CR) or Partial Response (PR) according to RECIST 1.1 as assessed by the investigator during routine follow up. Percentage of patients with Disease Control Rate (DCR) according to RECIST 1.1 as assessed by the investigator during routine follow up. Progression free survival (PFS) in patients with Stable Disease (SD), or PR, at the time of first dosing of ES2B-C001 alone or in combination with the adjuvant according to RECIST 1.1. Disease-free survival (DFS) in patients with CR at the time of first dosing of ES2B-C001 alone or in combination with the adjuvant according to RECIST 1.1. Overall survival (OS) 			

4 Trial Design

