9.1 Sample Size Determination

This is a phase I study following a traditional 3+3 design, and no formal statistical hypothesis will be tested. The sample size was estimated to be 9 evaluable patients assuming 3 possible dose levels. However, due to the cohort expansion design, a maximum of 27 evaluable patients in total could be dosed.

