9.3.1 Primary endpoint analysis

Total number and incidence of dose limiting toxicities (DLTs), number of patients with DTLs and percentage of patients with DLTs in each dose level and patient population will be reported.

Additionally, the number of DLTs, affected patients and percentage of affected patients will also be reported by preferred term and severity according to CTCAE v5.0 in each dose level and patient population.

The maximum tolerated dose will be determined for each patient population separately as lowest dose level at which ≥33% of patients have record of DLT.

The primary endpoint will be evaluated on the Safety Set.

Clinical Study: ES2B-C001-S01 EU CT No.: 2024-516333-12-00

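### Section 4.2 names the highest dose given as the MTD when no toxicity limit is found, while Section 9.3.1 yields no MTD from the same data

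*Protocol*

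**What the plan says.** The primary objective in Protocol Section 3, Table 3 is "To determine the safety, tolerability, maximum tolerated dose (MTD) for ES2B-C001 alone or in combination with the adjuvant".

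Two current sections say how the MTD is obtained:

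- Section 4.2 has a fallback: "if no unacceptable side effects or DLTs occur up to the highest dose level cohort", then "MTD will be determined as the maximum administered dose (MAD) level".
- Section 9.3.1 defines the MTD, for the primary endpoint analysis, as the "lowest dose level at which ≥33% of patients have record of DLT".

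On cohort size, Section 4.1 states "The number of patients included in one dose cohort is 3", with an option to go to 6 or 9. The synopsis has "9 patients (3 per cohort) will be enrolled in the dose escalation parts with 3 dose levels each". Section 9.1 gives the same base number and allows "a maximum of 27 evaluable patients in total could be dosed" with expansion. Section 4.3.1 makes three further patients obligatory after one DLT among the first three. The synopsis leaves other expansion to judgement, on grounds of variable immunogenicity data or a wish for more safety data.

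Section 9.1.1 lists, among its illustrative scenarios, one in which the true MTD lies above every tested dose.

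**The concern.** A trial that escalates to its top level without a DLT has not found a toxicity limit. It has shown that any limit lies above the tested range, or that too few patients were treated to see it. Calling the top dose the MTD makes two claims: that this dose was shown to be tolerated, and that it is the highest dose that is. The first may rest on very few patients, and the second has no data behind it.

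Section 4.2 says the trial is meant to inform the tolerated dose for the next phase, so the label would be carried forward. Because Section 9.3.1 produces no MTD from the same data, the answer to a primary objective would depend on which section the author of the report applies.

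**Working it through.** **The plan's own counts.** Three levels with 3 patients each give 3 × 3 = 9, the base number in Section 9.1. Three levels with 9 each give 3 × 9 = 27, the stated maximum. Both reproduce. The base number is thus the path with three patients at every level, which is the path followed when no DLT occurs and no optional expansion is used. The contents of Table 14 are not shown and could not be checked.

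**The two rules on the same data.** Take 0 DLTs at every level and no unacceptable side effects.

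- Section 4.2: the MTD is the highest dose administered.
- Section 9.3.1: the DLT proportion is 0% at each level, none reaches 33%, and no MTD exists.
- Section 9.1.1, scenario with the true MTD above the range: if no DLT is seen, Section 4.2 names a tested dose as the MTD, which is wrong by the scenario's own premise.

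**What zero DLTs in n patients supports.** The exact upper bound is 1 − 0.05^(1/n) for one-sided 95%, and 1 − 0.025^(1/n) for the upper limit of a two-sided 95% interval. The chance of seeing 0/n at a true rate p is (1 − p)^n.

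| Top level | One-sided 95% bound | Two-sided upper limit | Chance of 0/n if p = 1/3 | Chance of 0/n if p = 40% |
|---|---|---|---|---|
| 0/3 | 63.2% | 70.8% | 29.6% | 21.6% |
| 0/6 | 39.3% | 45.9% | 8.8% | 4.7% |
| 0/9 | 28.3% | 33.6% | 2.6% | 1.0% |

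For example, 1 − 0.05^(1/3) = 0.632 and (2/3)^3 = 0.296. With three patients, a rate well above the protocol's own 33% mark is not excluded. With nine, the one-sided bound falls below that mark, so the claim that the dose is tolerated gains support. The claim that it is the maximum gains none at any n, because no higher dose was tested.

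**How often it could occur.** The documents give no visible DLT rates, so these are assumptions, taken as equal at all levels with nine patients:

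- 5%: 0.95^9 = 0.630
- 10%: 0.90^9 = 0.387
- 20%: 0.80^9 = 0.134

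These are upper figures for the fallback in Section 4.2, which also requires that no unacceptable side effects occur. Optional expansion would lower them further. The 63% here and the 63% bound for 0/3 are unrelated quantities.

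**The case against.** The strongest reply is that MTD = MAD is an openly declared label. Anyone who reads Section 4.2 knows that no limit was found. Section 9.3.1 already requires the number and percentage of patients with DLTs at each level, so the 0/3 would stand beside any MTD statement. Escalation itself is unaffected. Most of this stands: nothing is hidden, and the harm is over-interpretation of a primary result. It does not remove the disagreement between two current sections.

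Three further objections stand in part:

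- **Cohort size.** 0/3 is the minimum case. Cohorts may grow to 6 or 9 without amendment, including for safety, and the DSMB may recommend more patients (Section 10.7). Figure 2 is not shown and the DSMB charter is a separate document, so either may address the size of the top cohort. What can be said is that the visible text requires no expansion before the label is applied.
- **Exact intervals.** Section 9.2 makes the DLT analysis descriptive, without inference. Leaving out exact intervals is not an error.
- **Likelihood.** A reader might infer that a vaccine of this kind will probably show no DLT, so that the fallback is the expected result. The documents do not support that. Section 2.1.3 reports only rare grade 3 toxicity with other HER2 vaccines. Section 2.3, however, calls the clinical safety profile unknown and reports poor local tolerance of the adjuvanted product in the toxicity study. The DLT list in Section 4.3.2 also covers injection-site reactions, LVEF decrease and related treatment delay.

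**Conclusion.** The point holds as a defect in how a primary conclusion is defined and labelled. Section 4.2 turns the absence of a finding into a named MTD, Section 9.3.1 gives no MTD from the same data, and Section 9.1.1 allows that the true MTD may lie beyond the range.

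The evidence behind the label can be as thin as 0/3, with a one-sided 95% upper bound of 63% and about a 30% chance of arising at a true 33% DLT rate. It could be 0/6 or 0/9 if expansion is used. The frequency of the no-DLT outcome is unknown; the 13% to 63% range rests wholly on assumed rates of 20% down to 5%.

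It would go too far to say that the trial will name its MTD on three patients, or that the rule alters escalation. The first is only the lower end of what the visible text permits, and nothing in the documents supports the second.

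**What to change.** Reconcile Sections 4.2 and 9.3.1 so that one MTD definition governs the primary conclusion, and let it state what is reported when no tested level meets it. Adding a sentence to 9.3.1 is not enough, because its rule must itself be squared with the rest of the protocol. It names a level at which at least 33% of patients had a DLT, whereas under Section 4.3.1 two or more DLTs in six patients (2/6 = 33.3%) bar further escalation, and Section 7.5 halts enrolment at that level if the DLTs are confirmed.

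For the no-DLT outcome, replace the fallback in Section 4.2 with wording such as: *MTD not reached; highest dose administered (MAD) reported*. Place it beside the DLT count and denominator per level that Section 9.3.1 already plans. An exact interval is optional.

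The cost is a short text change and a slightly less favourable headline claim. Doses, escalation steps and patient numbers stay as they are.

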4.3 Dose escalation

A DSMB will be appointed to oversee the trial. The composition and responsibilities of the DSMB is described in a dedicated charter, which will include additional instructions for the dose escalation procedure.

The decision to escalate the dose to the next dosing cohort or initiate the expansion part will be taken by the sponsor based on the DSMB recommendations. For the decision of dose escalation, AEs collected during the DLT period will be assessed by the DSMB. Other available data beyond the DLT evaluation period for all patients in the trial will also be assessed before a decision on escalation to the next dose level can be taken. Dose escalation rules will be based on the number of patients with AEs, specifically DLTs (Section 4.3.2). The DSMB will base recommendations on an evaluation of accumulated safety data and may include other available data, including data on immunogenicity (antibody titers) in their review.

Patients who discontinue for reasons other than toxicity before having DLT evaluable safety data may be replaced at sponsor's discretion.

A schedule of trial procedures is provided in Section 1.3. The administration of adjuvanted and non-adjuvanted ES2B-C001 is described in Section 6 and the trial assessments are described in Section 8.

The dose escalation will include 3 planned dose level cohorts with adjuvanted ES2B-C001 (Section 6.2).

Enrollment will be fully staggered in each of the populations, meaning that an observation period of 3 weeks plus 24 hours is foreseen before the second patient is dosed in one cohort. Dosing of the next subject in each cohort should not take place until 1 week after the preceding patient has received the first dose. Prior to dosing the second patient, safety and reactogenicity data from the previous patient will be discussed at a pre-dosing call between PI(s), CRO medical monitor, and

Clinical Study: ES2B-C001-S01 EU CT No.: 2024-516333-12-00

Sponsor. At subsequent administrations, pre-dosing calls will be scheduled if safety concerns warrant it. This will ensure an evaluation of safety prior to administration of the next patients.

Any safety concerns, such as potential DLTs and/or events that may meet a criterion for initiation of rescue medication, will be escalated to the DSMB who will review accumulated safety data and may provide recommendations for trial adjustments e.g., applying additional overnight stays for patients.

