	 Total anti-HER2 Immunoglobulin titers in sera by enzyme-linked immunosorbent assay (ELISA). Isotyping of anti-HER2 Immunoglobulins in sera (e.g. IgM, IgG (IgG1-4), IgD, IgE, IgA). Exploratory Endpoints: Percentage of patients with measurable disease at baseline achieving Complete Remission (CR) or Partial Response (PR) according to RECIST 1.1 as assessed by the investigator during routine follow up. Percentage of patients with Disease Control Rate (DCR) according to RECIST 1.1 as assessed by the investigator during routine follow up. Progression free survival (PFS) in patients with Stable Disease (SD), or PR, at the time of first dosing of ES2B-C001 alone or in combination with the adjuvant according to RECIST 1.1. Disease-free survival (DFS) in patients with CR at the time of first dosing of ES2B-C001 alone or in combination with the adjuvant according to RECIST 1.1. Overall survival (OS). This dose escalation part will be conducted according to an adapted 3+3
Study Period	 design. For each patient enrolled, there will be a: Screening period between 1 and 28 days prior to the first dose ES2B-C001. An out-patient treatment period of 12 weeks; Safety follow-up for ~6 weeks following the last dose of ES2B-C001. An end-of-study visit.
Study Design	The trial is a first-in-human, phase I, open-label, dose-escalating trial to assess the safety and tolerability of ES2B-C001 combined with [adjuvant] or without [adjuvant], in patients with human epidermal growth factor receptor 2 (HER2) expressing metastatic breast cancer.

Clinical Study: ES2B-C001-S01 EU CT No.: 2024-516333-12-00

Clinical Study: ES2B-C001-S01 EU CT No.: 2024-516333-12-00

The decision to escalate the dose to the next dosing cohort or initiate the expansion part will be taken by the sponsor based on the data safety monitoring board (DSMB) recommendations. The DSMB will base their recommendations on an evaluation of accumulated safety data and, if available, on immunogenicity data (antibody titers), whenever 3 patients of a specific cohort have received at least one dose, and the last patient completed the DLT observation period of 8 weeks.

Enrollment will be fully staggered in each of the populations, meaning that an observation period of 3 weeks plus 24 hours is foreseen before the second patient is dosed in one cohort. Dosing of the next subject in each cohort should ideally not take place until 1 week after the preceding patient has received the first dose.

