4.3.1 Dose escalation rules

Dose escalation to a higher dose will be driven by an evaluation by the DSMB. At the time of DSMB evaluation, the last patient in the current dose level cohort must have received the 2nd dose and must have accumulated safety data for 8 weeks following the first dose. This allows for the DLT evaluation period to include an assessment of a potential delay in dose 2 due to toxicity concerns, as described for DLT number 5 in Section 4.3.2.

If one of the 3 patients in a dosing cohort experiences a DLT, 3 additional patients are added to the same dose level cohort. If 2 or more patients among these 6 patients experience DLTs, no further dose escalation can occur, and lower dose levels can be further explored. Dose escalation will continue until not more than 1 out of 6 patients experience DLT in a dose level cohort or the highest dose level group has completed treatment or no trial stopping criterion has been met. See Figure 2.

[figure not shown]

Figure 2: Dose-escalation according to a 3+3 design

Dose escalation will continue until not more than 1 out of 6 patients experiences a DLT in a dose level cohort (see DLT definitions in Section 4.3.2) or the dose level of

Clinical Study: ES2B-C001-S01 EU CT No.: 2024-516333-12-00

treatment has been completed (maximum administered dose MAD) or a trial stopping criterion has been met. The stopping criteria for dose escalation and trial are provided in Section 7.

Patients experiencing DLT will have their administration of adjuvanted or non-adjuvanted ES2B-C001 discontinued. These patients are allowed to remain in the trial to follow safety, disease progression and immune response. The DSMB will convene and recommend whether a re-start of these patients' treatment is advised and if a dose reduction may be required.

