7.1 Discontinuation of Trial Treatment

Patients may stop treatment at any time during the trial at their discretion. The treating physician may, for safety reasons or the well-being of the patient, refrain from dosing at the discretion of the treating physician.

If adjuvanted or non-adjuvanted ES2B-C001 is permanently discontinued, the patient should, if at all possible, have an early termination visit and remain in the trial for follow-up visit 7 and 8. See the SoA (Section 1.3) for data to be collected at the End of Trial and during follow-up.

Discontinuation of trial treatment does not represent withdrawal from the trial.

Patients who discontinue for reasons other than toxicity before having DLT evaluable safety data may be replaced at sponsor's discretion.

A patient should be considered for discontinuation from trial treatment but continue to be monitored in the trial for any of the following reasons:

- Unacceptable toxicity.
- Intercurrent illness of sufficient magnitude to preclude safe continuation of the trial.
- Investigator's judgement on optimal benefit/risk not supporting continuation of the trial for the individual patient.
- Non-compliance with trial requirements (e.g. treatment delay of 28 days or more).
- · Patient's decision.
- Pregnancy during the trial.
- Patient is lost to follow-up.
- Death.

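### Optional replacement and a last-patient-only review condition let a cohort meet the written escalation conditions with 2 DLT-evaluable patients, although the trial is sized at 3 per level

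*Protocol*

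**What the plan says.** **Replacement.** Section 4.3 states: "Patients who discontinue for reasons other than toxicity before having DLT evaluable safety data may be replaced at sponsor's discretion". Section 7.1 repeats it ("before having DLT evaluable safety data may be replaced at sponsor's discretion").

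**When the DSMB reviews a cohort.** The synopsis (1.1) places the review "whenever 3 patients of a specific cohort have received at least one dose, and the last patient completed the DLT observation period of 8 weeks". Section 4.3.1 says that "the last patient in the current dose level cohort must have received the 2nd dose and must have accumulated safety data for 8 weeks" after the first dose. Both attach the completed window to the last patient. Neither states a condition on the follow-up of the other two.

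**What is counted.** The 3+3 rule in 4.3.1 counts patients in the cohort and does not mention evaluability. No visible text defines DLT-evaluable. The Safety Set in 9.2, used for the DLT analyses, takes anyone with at least one dose, so it does not supply the definition.

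**Sizing.** Section 9.1 says: "The sample size was estimated to be 9 evaluable patients assuming 3 possible dose levels", and that with expansion "a maximum of 27 evaluable patients in total could be dosed". Section 9.1.1 derives the operating characteristics from the pathways of the standard 3+3 design.

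**The concern.** A 3+3 design takes its error rates from the number of patients fully observed at each decision. Section 9.1 counts in evaluable patients, while the sections that govern conduct do not secure that number. A patient who withdraws or is lost during the 8-week window contributes only partial DLT information. If that patient is not replaced, the cohort is still a cohort of 3 by enrolment, and no DLT among 2 fully observed patients is read as no DLT among 3. In a first-in-human trial this makes it easier to escalate past a level that is too toxic, and the behaviour described in 9.1.1 need not be the behaviour of the trial as run.

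**Working it through.** **1. The plan's own figure.** 3 levels × 3 patients = 9, and 3 levels × 9 patients = 27. Both match 9.1 and the cohort sizes in 4.1 ("The number of patients included in one dose cohort is 3 but may be increased from n=3 to n=6 or n=9"). Three evaluable patients per level is therefore implied by 9.1, though not stated in those words.

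**2. Can a cohort with 2 evaluable patients pass the written conditions?** Suppose patient 1 or 2 receives dose 1 and then withdraws (7.3) or is lost to follow-up (7.4) before 8 weeks.
- Three patients with at least one dose (1.1): met.
- Last patient has completed 8 weeks (1.1, 4.3.1): met by patient 3.
- Last patient has received the second dose (4.3.1): met by patient 3.
- Replacement (4.3, 7.1): optional, so it may be declined.

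Every written condition holds with 2 evaluable patients. If patient 3 is the one who leaves, the last-patient condition fails. The gap therefore runs through patients 1 and 2 only.

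**3. Effect on the escalation probability.** The true DLT rates p are assumptions, because the scenario values of Table 14 are not visible. With n evaluable patients in the first group, and 3 further evaluable patients after a single DLT:

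P(escalate) = (1−p)^n + n·p·(1−p)^(n−1) × (1−p)^3

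| p | n = 3 | n = 2 |
|---|---|---|
| 1/3 | 0.2963 + 0.4444 × 0.2963 = 0.428 | 0.4444 + 0.4444 × 0.2963 = 0.576 |
| 0.5 | 0.125 + 0.375 × 0.125 = 0.172 | 0.25 + 0.5 × 0.125 = 0.3125 |

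With p = 0.33 instead of 1/3 the first row is 0.434 and 0.582. Either way it rounds to 43% and 58%. The second row rounds to 17% and 31%.

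**4. How often patient 1 or 2 is unevaluable.** The protocol gives no dropout rate. Assume each patient is independently unevaluable with probability d.

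P(at least one of patients 1 and 2) = 1 − (1−d)²
- d = 5%: 1 − 0.95² = 0.0975, about 10%
- d = 10%: 1 − 0.90² = 0.19
- d = 20%: 1 − 0.80² = 0.36

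These are chances that the situation arises in a given cohort. For escalation on 2 patients, the sponsor must also decline to replace and the DSMB must still recommend going up.

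**The case against.** **Staggered enrolment.** Patient 2 waits 3 weeks plus 24 hours, and the next patient at least a further week (4.3). When the last patient reaches 8 weeks, every earlier patient still in the trial is past 8 weeks. This stands. The last-patient wording matters only for patients who have left, so it is the other half of the replacement problem and not a separate defect.

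**Stopping treatment is not leaving the trial.** Section 7.1 says so and asks such patients to stay for follow-up if possible. The DLT window in 4.3.2 runs 8 weeks from the first administration and does not itself require a second dose. This also stands. A reader might infer that anyone who stops after dose 1, for progression or by choice, is unevaluable. The documents do not support that, and the clear case is withdrawal or loss within 8 weeks.

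**Other safeguards.** The protocol states 3+3 as its design. The sponsor decides on the DSMB's recommendation, the DSMB may recommend more patients for a cohort (10.7), and the charter will hold further escalation instructions (4.3). A minimum could be set there. This limits the claim to what the protocol itself allows. It does not close the gap, because the protocol fixes the replacement and review conditions and sets no minimum.

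**Biased replacement.** A reader might infer that a sponsor who knows the cohort's results would bias the DLT frequency through its choice to replace. The protocol does not say when that choice is made, and neither a direction nor a size can be shown. The point does not rest on it.

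**Conclusion.** The point holds as an inconsistency within the protocol. Sections 1.1, 4.3, 4.3.1 and 7.1 together permit escalation with 2 evaluable patients, whereas 9.1 and 9.1.1 presuppose 3 per level. The inconsistency does not depend on any assumed rate. Its size does: 43% to 58% at a true DLT rate of 33% and 17% to 31% at 50%, with at least one of patients 1 and 2 unevaluable in 10% to 36% of cohorts for d between 5% and 20%. These figures assume independent patients, a standard 3+3 decision rule and evaluable added patients.

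Two stronger readings should be resisted. The text would also let a cohort through with a single evaluable patient, but both patients 1 and 2 would have to be lost (d² = 0.25%, 1% or 4%) and both replacements declined, so that case is remote. Nor should the frequency be computed over all three patients, since losing the last one blocks the review. The protocol does not show that escalation on 2 patients will happen, only that nothing in it prevents this.

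**What to change.** Reconcile 1.1, 4.3, 4.3.1 and 7.1 with 9.1:
- Define DLT-evaluable, and say whether a patient who stops treatment but is followed for 8 weeks qualifies.
- In 4.3 and 7.1, state that a patient who is not DLT-evaluable will be replaced unless the level is already closed by DLTs.
- In 1.1 and 4.3.1, require that every patient counted in the escalation decision (3, or 6 after expansion) has either had a DLT or completed the 8-week window as evaluable. Use the same condition in both places; at present only 4.3.1 mentions the second dose.
- Carry the same minimum into the DSMB charter.

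The cost is protocol wording, an occasional replacement patient and some weeks of delay. The synopsis already places replacements for dropouts outside the total of 27, so the stated maximum does not change.
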